3 OBJECTIVES AND ENDPOINTS

Table 4 Objectives and Endpoints

Objectives	Endpoints
Primary	

 To evaluate the efficacy of triptorelin pamoate 22.5 mg 6-month formulation in achieving castrate levels of testosterone To evaluate the efficacy of triptorelin pamoate 22.5 mg 6-month formulation in maintaining the castrate levels of serum testosterone 	
 Percentage of participants achieving castrate levels of serum testosterone (<50 ng/dL or 1.735 nmol/L) on Day 29 Percentage of participants maintaining the castrate levels from Week 8 to Week 24
Secondary	

 To assess the safety profile including local tolerability of triptorelin pamoate 22.5 mg 6-month formulation 	
 Incidence of TEAEs (including local tolerability) throughout the study i.e., up to Week 24 Change from baseline in clinical safety laboratory parameters (blood chemistry and haematology) at Week 24 Change from baseline in physical examination at Day 1, Week 12 and Week 24 Change from baseline in ECG at Week 4 and Week 24 Change from baseline in vital signs (blood pressure and heart rate) at each visit up to Week 24

 To demonstrate the effect of triptorelin pamoate 22.5 mg 6-month formulation on PSA response 	
 Percent change in PSA from baseline (prior to injection) at Week 12 and Week 24 (percent change in PSA is defined as the absolute value of difference between the PSA values at Week 12 and Week 24 and the baseline value divided by the baseline value)

 To assess the PK of triptorelin pamoate 22.5 mg 6-month formulation in a subset of 12 participants 	
 PK parameters for dosing interval up to 24 weeks: 
 t_{max} C_{max} AUC_{0-169} AUC_{last}

 To assess the PD of testosterone in a subset of 12 participants 	
 PD parameters for dosing interval up to 24 weeks: 
 t_{max} C_{max} t_{cast}

 To assess the PK of triptorelin pamoate 22.5 mg 6-month formulation for all participants 	
 Sparse plasma concentrations of triptorelin at pre-dose and post-dose at Weeks 4, 8, 12, 16, 20 and 24

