5.2 Exclusion Criteria

Participants are excluded from the study if any of the following criteria apply:

Medical conditions

1. Risk of a serious complication in the case of tumour flare (known or suspicion of vertebral metastases threatening spinal cord compression or significant obstructive uropathy).
2. Presence of another neoplastic lesion or brain metastases.
- 3a. Previous history of QT prolongation or concomitant use of medicinal products known to prolong the QT interval or with a known risk of torsades de pointes.
- 4a. Metastatic hormone-sensitive prostate cancer with high tumour burden.
(Note: high tumour burden: presence of visceral metastases and/or at least four bone lesions with at least one lesion outside the vertebral column and/or pelvis per CHAARTED study (Kyriakopoulos 2018).)

5. Metastatic castration-resistant prostate cancer.

Prior/concomitant therapy

6. Previous surgical castration.

- 7a. Previous hormone therapy (including abiraterone) for prostate cancer within 6 months prior to study screening.
- 8a. Previous cytotoxic chemotherapy treatment within 6 months prior to study screening.
- 9a. Use of finasteride or dutasteride within 2 months prior to study screening.
10. Previous hypophysectomy or adrenalectomy.
- 11a. Any current use or use within 6 months prior to treatment start of medications which are known to affect the metabolism and/or secretion of androgenic hormones: ketoconazole, aminoglutethimide, oestrogens and antiandrogens.
Note: antiandrogen: enzalutamide, apalutamide or darolutamide is allowed (if required per investigator's clinical judgement) due to no interference on the metabolism and/or secretion of androgenic hormones.
- 12a. Current use of systemic or inhaled corticosteroids (topical application permitted).
13. Any previous use of traditional Chinese medicine or herbal products within 1 month prior to study screening or planned use during the study of products, which are known to have cytotoxic effect or affect the metabolism and/or secretion of androgenic hormones.

Prior/concurrent clinical study experience

- 14a. Participation in another study with an investigational drug or treatment within 3 months prior to study screening or within 5 drug half-lives of the investigational drug (whichever is the longer).

Diagnostic assessments

15. Severe kidney or liver impairment (creatinine >2 x upper limit of normal (ULN), aspartate aminotransferase (AST) and alanine aminotransferase (ALT) >3 x ULN).

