6.8 Concomitant Therapy

Any medication (excluding prior disease-specific medications) or vaccine (including over the counter prescription medicines, recreational drugs, vitamins, and/or herbal supplements) that the participant had received within 2 months before triptorelin administration or receives during the study must be recorded on the eCRF along with:

- Generic or trade name
- Reason for use
- Dates of administration including start and end dates
- Dosage information including dose, frequency and route of administration

The medical monitor should be contacted if there are any questions regarding concomitant or prior therapy.

The following concomitant medications are not permitted during this study:

- Any treatment or procedure with a specific or potential effect on androgenic hormones be administered concomitantly to the study drug (will be considered as a protocol violation). Per investigator's clinical judgement, suggest offering short-term administration of an older generation androgen receptor antagonist to M1 participants starting study intervention to reduce the risk of the 'flare-up' phenomenon.
- Any medication which raises prolactin levels and those affecting pituitary secretion of gonadotropins
- All drugs mentioned as prohibited in the exclusion criteria:
 - Finasteride or dutasteride.
 - Medications which are known to affect the metabolism and/or secretion of androgenic hormones: ketoconazole, aminoglutethimide, oestrogens.
 - Systemic or inhaled corticosteroids (topical application permitted).
 - Cytotoxic chemotherapy, abiraterone.
 - Any traditional Chinese medicine or herbal products previous used within 1 month prior to study start or plan to be used during the study, which are known to have cytotoxic effect or affect the metabolism and/or secretion of androgenic hormones.
 - Concomitant use of medications known to prolong QT interval should not be given (class IA (e.g. quinidine, disopyramide) or class III (e.g. amiodarone, sotalol, dofetilide, ibutilide) antiarrhythmic medicinal products, methadone, moxifloxacin, antipsychotics).

The following concomitant medications are permitted during this study, but they must be monitored closely, and every effort should be made to keep their dose and dose regimen constant throughout the course of the study:

- Analgesics: are allowed when necessary for pain relief.
- Anticonvulsants (e.g phenobarbital): long-term therapy may have additional risk for osteoporosis.

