8.3 Safety Assessments

Planned time points for all safety assessments are provided in the SoA. Evaluations obtained as part of routine medical care and performed during the screening period may be used in place of the study specific evaluations. Participants will acknowledge and agree to the possible use of this information for the study by giving informed consent.

8.3.1 *Physical Examinations*

A complete physical examination will include, at a minimum, assessments of the skin, and cardiovascular, respiratory, gastrointestinal and neurological systems. Height and weight will also be measured and recorded. Body weight will be measured in underwear and without shoes.

A brief physical examination will include, at a minimum, assessments of the lungs, cardiovascular system, abdomen (liver and spleen).

Investigators should pay special attention to clinical signs related to previous serious illnesses. Any clinically significant physical examination findings (abnormalities) observed during the study will be reported as AEs. Any physical examination findings (abnormalities) persisting at the end of the study will be followed by the investigator until resolution or until clinically stable. In addition, participants, particularly those with M1b status, should be advised regarding clinical signs suggestive of spinal cord compression.

8.3.2 *Vital Signs*

Blood pressure, temperature, respiratory rate and heart rate will be assessed as outlined in the SoA ([Section 1.3](#)) with an automated device (if possible) so that measurements are independent of the observer. Blood pressure and heart rate will be recorded after 5 minutes rest in supine or seated position. Absolute values and change from Baseline will be analysed. Any clinically significant vital signs will be recorded as AEs.

8.3.3 *Electrocardiograms*

A 12-lead ECG analysis will be included as a safety evaluation/endpoint in this study at timepoints described in [Table 1](#) and [Table 2](#).

A single 12-lead ECG will be recorded so that the different ECG intervals (RR, PR, QRS, QT, QTcF) can be measured automatically. The ECG will be recorded with the participant in supine position after five minutes of rest until four regular consecutive complexes are available.

Any clinically significant abnormalities will be recorded as AEs.

8.3.4 *Magnetic Resonance Imaging Scan*

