5.1 General Considerations

All statistical analyses will be performed using the Statistical Analysis System® software version 9.4 (or higher if available).

5.1.1 *Outputs Presentation*

5.1.1.1 *Tables Header*

Depending on the type of data, the summary tables will be presented as follows:

- For disposition, demographic and baseline data: by treatment group,
- For efficacy and safety data: by treatment group.

5.1.1.2 *Presentation of Treatment Group*

Tables, Figures and Listings (TFLs) will be displayed using the following treatment group label:
Triptorelin 6M

5.1.1.3 *Presentation of Visits / Timepoints*

Summaries by visit will be presented using visit number as collected in the Electronic Case Report Form (eCRF).

Visits in the TFLs will be presented as follows and in the following order:

Long Visit Name	Short Name
Screening	Scr
Baseline	Bsl
Day 1	D1
Day 2	D2
Day 3	D3
Day 5	D5
Day 8	D8
Day 15	D15
Day 22	D22
Week 4 Day 29	W4D29
Week 8 Day57	W8D57
Week 12 Day85	W12D85
Week 16 Day113	W16D113
Week 20 Day141	W20D141
End of Study/Early Withdrawal	EoS/EW

In the event a participant is enrolled, but does not receive study intervention, the participant will not remain in the study and EoS/EW assessment will not be performed.

5.1.2 *Descriptive Statistics*

All raw and derived variables will be listed and described using summary statistics. For categorical variables, summary statistics will be displayed using descriptive statistics by frequency count and percentages by category. The missing category will be presented if there is at least one missing category for at least one treatment group. Except otherwise specified, participants with missing data will be included in the calculation of percentages. For quantitative variables, summary statistics will be displayed using descriptive statistics by number of observations, mean, standard deviation (SD), median, minimum and maximum. Frequency and proportion of missing data will be displayed.

5.1.3 *Baseline Value*

Unless otherwise specified, baseline is defined as the last non-missing measurement taken prior to first Investigational Medicinal Product (IMP) administration (including unscheduled assessments).

5.1.4 *Reference Start Date and Study Day*

Reference start date is defined as the day of the first IMP administration.

The day of the first IMP administration will be Day 1. Study day will be calculated as:

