- A listing of all laboratory data. Out-of-reference-range values will be flagged as high (H) or low (L),
- A listing of all abnormal data.
- A listing of CTCAE grade 3 and higher values. All data for a laboratory parameter will be displayed for a participant who has any post-baseline value with CTCAE grade greater than or equal to 3 for the parameter.

5.8.5 ***Vital Signs***

Blood pressure, temperature, respiratory rate and heart rate will be assessed. Any clinically significant vital signs will be recorded as AEs. The following summaries are to be provided:

- A summary of the actual and change from baseline in each vital sign parameter by treatment group and visit,
- A shift from baseline to post-dose in interpretation of clinical significance (normal, abnormal, not clinically significant [NCS], abnormal, clinically significant [CS]).

The following listing are to be provided:

- A listing of vital sign data.
- Listing of all abnormal data.

5.8.6 ***Electrocardiogram (ECG)***

Results from the local lab units will be used.

The following quantitative ECG measurements will be taken during the study:

- heart rate (bpm),
- RR interval (msec),
- PR interval (msec),
- QRS interval (msec),
- QT interval (msec),

Fridericia corrected QT (QTcF) interval (msec) = $QT/\sqrt[3]{RR}$;

An overall Investigator assessment of ECG will be provided as “normal”, “abnormal NCS” and “abnormal CS”. Any clinically significant abnormalities will be recorded as AEs.

The following summaries of ECG data may be appropriate:

- A summary of the actual and change from baseline in each ECG parameter by treatment group and visit,
- A shift from baseline (normal vs. abnormal NCS vs. abnormal CS) to each post-baseline visit.

The following listing are to be provided:

- A listing of ECG data.
- A listing of all abnormal data.

5.8.7 ***Physical Examination***

The following summary and listings will be provided:

- A shift from baseline (normal vs abnormal NCS vs. abnormal CS) to each post-baseline visit by body system.
- A listing with any participants with at least one physical examination abnormality.

5.8.8 *Other*

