XXXX-XX-XX	Min ([First IMP admin.], AE end date)		Min (2002-08-11, AE end date)

YYYY = non-missing year, MM = non-missing month, DD = non-missing day, XX = missing field.

If AE end date is partial, imputation could be done assuming the latest possible date (i.e. last day of month if day unknown, or 31st of December if day and month are unknown).

A3. Programming Convention for Outputs

All text fields must be left justified and numeric or numeric with some text specification (e.g.: not done, unknown, <4.5, ...) must be decimal justified.

The mean, median, and SD will be reported to one decimal place greater than the raw data recorded in the database. The minimum and maximum values will be reported with the same number of decimal places as the raw data recorded in the database. In general, the maximum number of decimal places reported should be four for any summary statistic.

Percentages will be presented to one decimal place. Percentages will not be presented for zero counts. Percentage will be calculated using n as denominator. The denominator n will be specified in a footnote for clarification if necessary. If sample sizes are small, the data displays will show the percentages, but in the CSR only frequency counts should be described.

P-values will be reported to four decimal places (e.g.: p=0.0037), after rounding. P-values which are less than 0.0001 will be presented as '<0.0001'.

Dates will be presented in the format [ddMmmyyyy] and times in the format [hh:mm].

A4. Listings Conventions

Any listings will contain at least the following data: participant identifier, age and gender. When dates are presented, the associated study days should be included. They should be sorted by treatment group then participant identifier. For multicentre studies, listings should be broken down by centre and treatment group.

A5. EudraCT Categories for Age

For EudraCT results summaries, in addition to quantitative descriptive statistics of age, demographic tables should include presentation of age using the following EudraCT categories (as applicable):

Adults (18-64 years)
From 65 to 84 years
85 years and over

A6. CTCAE V5.0 Grading for Laboratory Values

Grade is classified based on the numeric lab result criteria in CTCAE v5.0 grading. The clinical criteria or condition will not be used.

Analytic	CTCAE SOC	CTCAE Term	Grade 1	Grade 2	Grade 3	Grade 4	Grade 5
Hematology							

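### SAP 5.8.6 plans no threshold summary of QTcF, so the number and percentage of men with a large prolongation will not be tabulated

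*SAP*

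**What the plan says.** The protocol treats QT as something to guard against. Exclusion criterion 3a (Protocol 5.2) covers "Previous history of QT prolongation or concomitant use of medicinal products known to prolong the QT interval", and Protocol 6.8 adds "Concomitant use of medications known to prolong QT interval should not be given".

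QTcF is collected: "A single 12-lead ECG will be recorded so that the different ECG intervals (RR, PR, QRS, QT, QTcF) can be measured automatically" (Protocol 8.3.3). One of the secondary safety endpoints is "Change from baseline in ECG at Week 4 and Week 24" (Protocol 3, Table 4). Footnote b of the schedule of activities also allows ECGs at other times when clinically indicated.

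The planned reporting is:
- SAP 5.8.6: "A summary of the actual and change from baseline in each ECG parameter by treatment group and visit".
- SAP 5.1.2, for quantitative variables in general: "number of observations, mean, standard deviation (SD), median, minimum and maximum". Nothing in 5.8.6 overrides this.
- SAP 5.8.6, for the investigator's overall read: "A shift from baseline (normal vs. abnormal NCS vs. abnormal CS) to each post-baseline visit".
- SAP 5.8.6: clinically significant abnormalities are recorded as AEs. SAP 5.8.3 tabulates TEAEs by SOC, PT and maximum CTCAE grade.
- SAP 5.8.6: listings of all ECG data and of abnormal data.

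SAP 6.2 restricts by-visit tables to scheduled visits. SAP 5.8.6 introduces its two ECG summaries only as possibly suitable, while Protocol 9.4.5 commits to summarising ECG values and changes at each visit. For laboratory data, SAP 5.8.4 plans shifts by CTCAE grade, and Appendix A6 states "Grade is classified based on the numeric lab result criteria in CTCAE v5.0 grading". That appendix covers haematology and biochemistry only.

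**The concern.** The clinical interest in QTcF lies in individual large values, so the natural questions are how many men had one and what share of those dosed they were. Neither planned ECG table answers them. The value-and-change table describes the centre, the spread and a single extreme at each end. The shift table follows one overall judgement that combines QT with every other ECG finding and has no numeric criterion. A man read as abnormal but not clinically significant at baseline for another reason, and read the same way after a large QTcF rise, shows no shift.

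At stake is the usefulness of a safety endpoint the trial already measures. If a few men have a large rise, the report would show that at least one did, but not how many. If none does, the report would not state the upper bound that the data support.

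**Working it through.** **Inputs from the documents.** Planned enrolment is 195 (Protocol 9.2, SAP 2.3). ECG summaries use the Safety Set, meaning all men dosed (SAP 4 and 5.8.1), so the denominator is about 195 rather than the 165 evaluable for efficacy. The plan's own inflation reproduces: 165/(1 − 0.15) = 194.1, rounded up to 195. The documents give no figure for QTcF variability and no QTcF limit.

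**Assumptions (not in the documents).** SD of QTcF change 10, 15 or 20 ms; a large increase of +60 ms (+70 ms in the simulation); all 195 men have a paired ECG.

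**1. Effect on the mean.** With k men at +60 ms, the mean shifts by 60k/195:
- k = 1: 0.31 ms
- k = 3: 0.92 ms
- k = 5: 1.54 ms

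For k = 3, f = 3/195 = 0.0154. The overall SD is √(SD² + 60²·f(1 − f)) = √(SD² + 54.5), which is 12.4, 16.7 or 21.3 ms. The 95% half-width for the mean, 1.96·SD/√195, is then 1.7, 2.3 or 3.0 ms. A shift of 0.92 ms cannot be distinguished from zero at any of these.

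**2. Effect on the maximum.** In 2,000 simulated sets of 195 changes per scenario, the average maximum with no outlier is about 27, 41 or 55 ms for SD 10, 15 or 20 ms. With one man at +70 ms it is about 70 ms at every SD, and with three men it is again about 70 ms. The mean is about 0.4 ms and 1.1 ms respectively. So the maximum reveals that a large increase occurred, but does not separate one man from three.

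**3. What a count table would show.** Exact (Clopper-Pearson) 95% intervals on 195:
- 1 man: 0.5% (0.01% to 2.8%)
- 3 men: 1.5% (0.3% to 4.4%)
- 5 men: 2.6% (0.8% to 5.9%)
- 0 men: upper limit 1 − 0.025^(1/195) = 1.9%

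**4. Where an individual prolongation would appear under the present plan.**
- Scheduled visit, the largest at that visit: as the maximum.
- Scheduled visit, not the largest: it contributes to the mean and SD, but is not identifiable as a case in the value-and-change table.
- Judged clinically significant: in the shift table if at a scheduled visit, and in the TEAE tables.
- Judged not clinically significant: at most as the maximum, or inside a shift category shared with all other ECG findings; otherwise only in listings.
- Unscheduled ECG not reported as an AE: only in listings. SAP 6.2 permits unscheduled measurements for a worst-value endpoint, but 5.8.6 defines no such ECG summary.

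**5. Noise in a change category.** With no drug effect, the expected share above +30 ms is P(Z > 30/SD):
- SD 10 ms: 0.1% (about 0.3 of 195)
- SD 15 ms: 2.3% (about 4)
- SD 20 ms: 6.7% (about 13)

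**The case against.** The strongest reply is that the plan already makes a large prolongation visible. SAP 5.1.2 requires the minimum and maximum, a clinically significant ECG becomes an AE counted by PT and CTCAE grade, and every value is listed. With about 195 men and two scheduled post-dose ECGs, cases can be found by reading the listings. All of this stands. A reader might infer from SAP 5.8.6 alone that QTcF is reported only as a mean change, or that a few affected men would appear in no table. The documents support neither inference.

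A reader might also take QT prolongation to be a risk named in the protocol's risk assessment. It is not: Protocol Table 3 lists cardiovascular events without naming QT, and both documents state that AEs of special interest do not apply. QT enters through the eligibility and concomitant-medication rules, which also remove men more likely to show it.

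Two further objections hold in part. Appendix A6 contains no QTcF limit, so the laboratory grading cannot simply be extended; cut-offs must be chosen and stated. And with one automatically measured ECG per visit and no control arm, lower change categories will count some normal variation (step 5).

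These replies do not supply a count. The maximum cannot give a number, the AE route depends on each site's judgement without a numeric criterion, and listings give no rate or denominator.

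**Conclusion.** The point holds as a reporting gap. A large QTcF prolongation at a scheduled visit would be seen as the maximum, but the number and percentage of men affected would not be tabulated. Beyond that maximum and the mixed overall read, prolongations judged not clinically significant could be seen only in listings. So could those found on unscheduled ECGs, unless reported as AEs.

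Under the stated assumptions, three affected men among about 195 shift the mean by 0.9 ms and give the same maximum as one man, while a count table would show 1.5% (0.3% to 4.4%). With none affected, it would support an upper limit of 1.9%. The percentages depend only on the counts and the denominator; the mean and maximum results depend on the assumed SD and effect size. The illustration is not a forecast that such cases will occur. No primary endpoint or efficacy conclusion is affected.

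The permissive wording in SAP 5.8.6 is a smaller matter. Protocol 9.4.5 already commits to the descriptive ECG summary, so the SAP needs to match it.

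**What to change.** In SAP 5.8.6, add one table on the Safety Set giving counts and percentages of participants by QTcF value category and by increase-from-baseline category. Present it by visit and for the worst post-baseline value, with unscheduled ECGs included in the worst value. The sponsor should pre-specify the cut-offs in the SAP before database lock, since Appendix A6 gives none for QTcF. They are reporting categories only and set no clinical rule.

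Reword the lead-in to the ECG summaries so that they are definitely provided, in line with Protocol 9.4.5.

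Settle the RR unit first. SAP 5.8.6 lists RR in msec and divides QT by its cube root; QT 400 with RR 1000 then gives 400/10 = 40 rather than 400, and no category would work on that scale.

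The cost is one extra table from data already collected. The drawback is that lower change categories will include some normal variation, which a footnote should say.

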5.7 Efficacy

5.7.1 General Considerations

The FAS and PPS will be used for efficacy analyses unless explicitly stated differently. Analysis on the FAS will be the primary analysis.

A listing of all efficacy data (raw and derived) will be provided (see listing detail conventions in Appendix A4). Descriptive statistics will be provided for all endpoints.

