5.7.2.2 Primary Analysis

The two primary endpoints will be tabulated with two-sided 95% CIs separately using the Clopper Pearson exact method for the FAS.

Castrate levels of serum testosterone will be summarized with descriptive statistics. Value below the lower limit of quantification (LLOQ) will be substituted by the LLOQ value for summary. Whether castrate level of serum testosterone is achieved (Yes/No) will also be summarized by visit.

Individual testosterone level data versus visit will be plotted by participant on a semi-logarithmic scale on the FAS with a dash line to indicate the testosterone limit of castration (50 ng/dL or 1.735 nmol/L) and a second dash line for the LLOQ. The arithmetic mean (\pm SD) and median testosterone levels versus visit will also be presented.

A testosterone level will be listed on all participants enrolled by participant and visit. All values below the limit of quantification will be listed as such.

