Local tolerance will be assessed 2 hours (± 15 minutes) after the single injection of 6-month formulation triptorelin, the injection site will be examined including but not limited to tenderness, erythema, swelling, haematoma, rash, pain, itching and induration. The presence of local tolerance will be listed and summarized for each symptom. The maximum length (mm) and width (mm) of presented symptom will also be summarized where applicable.

5.9 PK

5.9.1 *Triptorelin Plasma Concentrations*

Tables, listings and figures of triptorelin plasma concentrations will be generated by the SP for both the Rich PK Analysis Set and the Population PK Analysis Set.

Individual plasma concentrations of triptorelin will be listed and summarised by visit and time points using descriptive statistics for continuous variables including number of available observations (n), mean, median, SD, minimum, maximum, SEM, CV, geometric mean, geometric coefficient of variation (gCV) % (assuming log normally distributed data, and calculated as: $gCV\% = \text{SQRT}(e^{s^2}-1)*100$; where s is the SD of the log-transformed values) and 95% CI for mean.

Plasma concentrations should be displayed with the same precision than the LLOQ. In descriptive statistics, calculations derived from plasma concentrations (mean, minimum, maximum, median, SD etc.) should follow the same rule whereas CV% will only be displayed with one decimal digit.

Source data as reported from the laboratory will be used for calculation of concentration summary statistics. All values below or above a limit of detection (e.g. <0.1 or >100) will be listed as such. LLOQ will be presented as 'BLQ' in the listings and the LLOQ value presented as a footnote. Missing PK samples will be reported as no sample (NS) and/or not reportable (NR) and considered excluded from plasma concentration summary statistics. For summary tables, all BLQs will be considered as missing and will not be included in the summary statistics. The number of BLQs and non-BLQs at each scheduled time point will be reported. Summary Statistics will not be calculated if non-BLQ concentrations at a scheduled time point is less than 3 and if more than one third (1 out of every 3 values) are missing; in that case only minimum and maximum will be reported. Individual and mean triptorelin concentration time profiles, as well as spaghetti plots, will be generated.

5.9.2 *Triptorelin PK Analysis*

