5.10 Anti-drug Antibodies

Not applicable.

5.11 PD

5.11.1 *Testosterone Serum Concentrations*

Tables, listings and figures of testosterone serum concentrations will be generated by the SP for both the FAS and the Rich PD Analysis Set, following the same conditions described in 5.9.1 for triptorelin plasma concentrations.

5.11.2 *Testosterone PD Analysis*

The PD analyses of testosterone serum concentrations for the Rich PD Analyses Set will be performed by NCA. The NCA analysis will be described in a separate analysis plan and reported in a standalone report.

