6 DATA HANDLING

6.1 Visit Window

Unless otherwise specified, no time window for visit/timepoints will be needed for analyses.

6.2 Unscheduled Visits, Retest, Withdrawal Visit,

All listings will include retests and unscheduled visits, while for the description by visit in the tables, only the scheduled visits according to the protocol will be described.

Unscheduled visit and retest measurements will be used to provide a measurement for a baseline data or endpoint value (e.g. worst value), if appropriate according to their definition. These measurements will also be used to determine abnormal laboratory, vital signs values or ECG.

If a value requires a retest (for laboratory values, vital signs and ECG) the closest non-missing reliable value to the scheduled visit will be used in the summary tables.

An assessment will be considered reliable if it is performed without any technical problem and if the result is within the range of likely values.

Participants who have withdrawn early from the study will have their last assessment entered at the end of study/early withdrawal visit in the eCRF. There is no remapping required for end of study/early withdrawal visit.

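### SAP 5.11.1 leaves below-LLOQ testosterone out of the FAS summary tables, SAP 5.7.2.2 sets the same values to the LLOQ, and neither document reconciles the two

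*SAP*

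**What the plan says.** - **SAP 5.11.1** has testosterone tables, listings and figures produced for the FAS and for the Rich PD Analysis Set, "following the same conditions described in 5.9.1 for triptorelin plasma concentrations".
- **SAP 5.9.1**, the section referred to, says: "For summary tables, all BLQs will be considered as missing and will not be included in the summary statistics". It adds: "The number of BLQs and non-BLQs at each scheduled time point will be reported". It also withholds summary statistics other than the minimum and maximum when fewer than three values are quantified and more than a third are missing.
- **SAP 5.7.2.2** also summarises serum testosterone descriptively, under a different rule: "Value below the lower limit of quantification (LLOQ) will be substituted by the LLOQ value for summary". For listings: "All values below the limit of quantification will be listed as such".
- **SAP 5.7.1** sets the population for that efficacy summary: "The FAS and PPS will be used for efficacy analyses unless explicitly stated differently".
- **SAP 6.2** says that in by-visit tables "only the scheduled visits according to the protocol will be described".

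SAP 2.6, which lists departures from the protocol, covers only the analysis set for medical history and medications. Protocol 9.4.3.2 asks for testosterone summaries by visit and gives no BLQ rule.

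**The concern.** At each scheduled visit, the FAS testosterone values enter two summaries under two BLQ rules. One discards BLQ values and the other keeps them at the LLOQ. The discarding is informative: the drug is meant to suppress testosterone, so BLQ values would come from the most suppressed participants. The rule was written for triptorelin and reaches testosterone only by cross-reference, with no reason given.

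Serum testosterone in all participants is a stated secondary endpoint (Protocol section 3). The study report could carry two FAS summaries of it with different n, different means and usually different minima. A reader would have no explanation, and the higher mean would understate suppression. Only post-dose visits are exposed, because eligibility requires testosterone above 150 ng/dL (Protocol 5.1) and a pre-dose BLQ value is implausible.

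**Working it through.** The plan states no figure on this point that could be reproduced, so the check is algebra followed by illustration.

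**1. Same values in both tables.** SAP 5.7.1 makes the FAS an efficacy set, SAP 5.11.1 names the FAS, and SAP 6.2 restricts by-visit tables to scheduled visits.

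**2. Gap between the means.** At one visit, let f be the BLQ share, m the mean of the quantified values and L the LLOQ.

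- 5.11.1 mean = m
- 5.7.2.2 mean = (1 − f)m + fL
- Gap = m − [(1 − f)m + fL] = f(m − L)

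The gap is positive whenever f > 0 and some quantified value exceeds L. Against the true mean, exclusion is always upward, because every dropped value lies below every retained one. Substitution is also upward, but less so.

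**3. Relative size without a distribution.** With k = m/L, the gap relative to the 5.7.2.2 mean is f(k − 1)/[f + (1 − f)k]. As k grows it approaches, but never exceeds, f/(1 − f). For assumed f and k:

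| f | k = 2 | k = 3 | k = 5 | ceiling f/(1 − f) |
|---|---|---|---|---|
| 1% | 0.5% | 0.7% | 0.8% | 1.0% |
| 5% | 2.6% | 3.4% | 4.2% | 5.3% |
| 10% | 5.3% | 7.1% | 8.7% | 11.1% |

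One BLQ value among an assumed 165 has a ceiling of 1/164 = 0.6%.

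**4. Illustration by LLOQ.** The documents give no LLOQ, BLQ share or distribution. Assume post-dose testosterone is log-normal with geometric mean 10 ng/dL and geometric SD 2. The true mean is then 10 × exp[(ln 2)²/2] = 12.72 ng/dL.

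| Assumed LLOQ (ng/dL) | BLQ share | 5.11.1 mean | 5.7.2.2 mean | Gap |
|---|---|---|---|---|
| 1 | 0.04% | 12.72 | 12.72 | 0.04% |
| 2 | 1.0% | 12.83 | 12.72 | 0.9% |
| 5 | 15.9% | 14.43 | 12.93 | 11.6% |

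At LLOQ 5 the identity gives 0.159 × (14.43 − 5) = 1.50, which matches 14.43 − 12.93. There, exclusion overstates the true mean by 13.5% and substitution by 1.7%.

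With geometric SD from 1.5 to 2.5, the gap runs from 0% to 0.6% at LLOQ 1, from 0% to 3.6% at LLOQ 2, and from 2.5% to 20% at LLOQ 5.

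**5. Does the suppression rule remove the conflict?** It needs fewer than three quantified values: at least 163 BLQ of an assumed 165, or at least 10 of 12 in the rich-sampling subset. It is unlikely to act in the FAS tables.

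**The case against.** The strongest reply is that each rule is clear for its own table. A programmer can build both without guessing, and an efficacy section and a concentration section may follow different conventions. The exclusion is also visible: BLQ and non-BLQ counts are reported, BLQ values are listed as such, the individual plots carry an LLOQ line, and castrate status is shown by visit. The SAP announces a separate shell document, which might carry a footnote on BLQ handling. The assay is described as sensitive (Protocol 8.2.1), so BLQ values may be rare.

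Much of this stands. The plan is workable, the effect may be nil, and the missing explanation can be asserted only for the protocol and SAP text. However, counts and listings disclose the exclusion without correcting the statistics, and no purpose is given for applying the triptorelin rule to testosterone.

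A reader might infer more than the documents support:

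- **That the co-primary results are affected.** They are not if the LLOQ is below 50 ng/dL, since a BLQ value is then castrate under either rule.
- **That the Rich PD tables conflict too.** SAP 5.7.2.2 produces no table for that set, so there is nothing to reconcile there.
- **That the geometric means disagree between tables.** The default statistics in SAP 5.1.2 include no geometric mean, so only the 5.11.1 table would show one.
- **That the mean profiles are distorted.** The exclusion rule is limited to summary tables. SAP 5.9.1 says only that "Individual and mean triptorelin concentration time profiles, as well as spaghetti plots, will be generated", not how BLQ values enter them.

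**Conclusion.** The inconsistency holds for the FAS testosterone tables and is minor. Followed as written, SAP 5.11.1 drops the most suppressed post-dose values whenever any are BLQ. Its mean is then biased upward and exceeds the SAP 5.7.2.2 mean by f(m − L), provided some quantified values exceed the LLOQ. The printed n also differs, as does the minimum unless a quantified value equals the LLOQ.

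The direction needs no distributional assumption; the size cannot be fixed from the documents. It is zero if nothing is BLQ, under 1% at an LLOQ of 1 or 2 ng/dL in the assumed base model, and 11.6% at 5 ng/dL. A claim that the distortion is large would rest wholly on an assumed LLOQ and distribution. The analysis is descriptive with no formal testing (SAP 5.7.1.1). That the co-primary percentages are safe assumes an LLOQ below 50 ng/dL.

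**What to change.** Add to SAP 5.11.1:

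*For the FAS testosterone summary tables, values below the LLOQ are set to the LLOQ, as in 5.7.2.2, instead of being treated as missing; the BLQ and non-BLQ counts are reported at each time point, and the suppression rule of 5.9.1 still applies, with BLQ values counted as not quantified for that rule.*

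The two FAS means then agree at every visit where both are shown. The suppression rule should stay. With 11 of 12 values BLQ at an assumed LLOQ of 5 ng/dL and one assumed value of 12 ng/dL, substitution alone would print a mean of 5.6 with a 95% CI of 4.3 to 6.9, built almost wholly on a constant.

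For the Rich PD set, the same substitution may be used if it agrees with the separate non-compartmental analysis plan and the suppression rule is kept. If the sponsor prefers to keep both rules, the minimum is to state why in the SAP and footnote the BLQ rule on each table.

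Cost: one sentence and no new data, since SAP 5.7.2.2 already requires the derivation and SAP 5.9.1 the counts. Downside: substitution still overstates the mean somewhat and compresses the SD at high BLQ rates, though it overstates the mean less than exclusion does.
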